I will provide copies of the protocol and all pertinent information to all individuals responsible to me who assist in the conduct of this study. I will discuss this material with them to ensure that they are fully informed regarding the study treatment, the conduct of the study, and the obligations of confidentiality.

[figure not shown]
Note: This document is signed electronically through submission and approval by the Principal Investigator in the University of Utah IRB Electronic Research Integrity and Compliance Administration (ERICA) system.

STUDY SUMMARY

Title	Propranolol Use for Treatment of Impaired Awareness of Hypoglycemia
Short Title	Propranolol in treating hypoglycemia unawareness
Protocol Number	IRB #: 00101995
IND	Exempted; IND 135258
Phase	II Pilot
Design	Double-blinded, placebo-controlled
Study Duration	Up to 2 years for pilot study
Study Center(s)	University of Utah Health
Objectives	To evaluate whether propranolol will both improve hypoglycemia awareness and also reduce hypoglycemia severity and duration in type 1 diabetes patients with impaired awareness of hypoglycemia
Number of Subjects	Twelve subjects for pilot study
Diagnosis and Main Eligibility Criteria	Type 1 diabetes patients with impaired awareness of hypoglycemia Inclusion: 
 • Type 1 diabetes for more than 5 years • Age between 21 to 59 years old • Hemoglobin A1C \leq 9% • No beta-blocker use in last 6 months Exclusion: 
 • Coronary, cerebral or peripheral vascular disease or other major cardiovascular diseases • Cardiac conduction abnormality or heart failure history • Advanced kidney/liver disease • Advanced diabetic microvascular complications • Contraindication, including hypersensitivity to beta-blockers
Study Product, Dose, Route, Regimen	Propranolol ER 80 mg oral daily or matching placebo oral daily
Duration of Administration	4 weeks of study drugs (propranolol ER or placebo)
Reference Therapy	Reference: Placebo

Statistical Methodology	The exact Wilcoxon rank sums test to determine study outcomes. Hodges-Lehman estimates and associated exact 95% confidence intervals will provide estimates of the size of the treatment effect.
-------------------------	--

STUDY SCHEMA

CGM, continuous glucose monitoring

1. OBJECTIVES

1.1 Primary Objective

- To determine whether propranolol increases the recognition of hypoglycemic events

1.2 Secondary Objectives

- To determine whether propranolol improves hypoglycemia awareness questionnaire scores;
- To establish if propranolol reduces hypoglycemia severity and duration;
- To assess if propranolol decreases in onset-to-diagnosis/treatment and diagnosis/treatment-to-recovery duration and total hypoglycemia/severe hypoglycemia frequency (total/day/night);
- To establish whether propranolol decreases fear of hypoglycemia; and
- To determine if propranolol decreases overall mean blood glucose value.

2 BACKGROUND

Type 1 diabetes mellitus (T1DM) can lead to serious and devastating complications, including microvascular (retinopathy, neuropathy and nephropathy) and cardiovascular disease. Both diabetic microvascular and cardiovascular complications can be reduced with intensive insulin therapy and strict blood glucose control which target hemoglobin A1C to less than 7%. [1] However, tighter glycemic control correlates with a higher incidence of hypoglycemia and severe hypoglycemia. [2] Recurring exposure to hypoglycemia leads to an attenuated sympathoadrenal response to hypoglycemia (which is termed hypoglycemia-associated autonomic failure), and thus a loss or decrease in neurogenic hypoglycemic symptoms (i.e. impaired awareness of hypoglycemia). [3, 4] Impaired awareness of hypoglycemia is associated with a six-fold increased risk of severe hypoglycemia [5] and physician or patient-directed higher glycemic goals. Impaired awareness of hypoglycemia is therefore a major barrier in diabetes management, by precluding optimal glycemic control and realization of its full benefits. [3]

Several therapeutic strategies have been proposed to improve hypoglycemia awareness in T1DM patients. A temporal increase in glycemic goal only sustains hypoglycemia awareness recovery for a short-term. [6, 7] Islet transplantation is invasive, extremely expensive and requires life-long use of immunosuppressants. [8] A widely available and affordable treatment with sustained efficacy for improving hypoglycemia awareness is therefore in urgent need. Pharmaceutical agents targeting potential mechanisms that contribute to the development of impaired hypoglycemia awareness have been proposed, including beta-blockers, opioid receptor antagonists and selective serotonin uptake inhibitors (SSRIs). [4] However, none of these agents has been approved for the treatment of impaired hypoglycemia awareness.

In the current study, we will examine the clinical use of beta-blockers, specifically propranolol, for the treatment of impaired hypoglycemia awareness. Prior rodent studies suggest that norepinephrine levels in the ventromedial hypothalamus (VMH) increase during an *acute* bout of hypoglycemia and that the *acute* activation of the VMH beta-2 adrenergic receptors enhances the

counterregulatory response to hypoglycemia. [9, 10] However, previous studies investigating the effects of *repeated* VMH noradrenergic system activation suggested that recurring hypoglycemia dampened the counterregulatory hormone response to hypoglycemia [11], possibly due to repeated activation of VMH beta2-adrenergic receptors [12]. In addition, carvedilol (a non-specific beta-blocker) prevented the onset of hypoglycemia-associated autonomic failure in rats made recurrently hypoglycemic ([name], personal communication). Consistent with these findings, propranolol, which blocks beta-2 adrenergic receptors, has been shown to prevent hypoglycemia-associated autonomic failure in healthy human subjects [13]. These studies suggest that the mechanisms which contribute to the development of hypoglycemia-associated autonomic failure may lie downstream of β_2 -adrenergic receptor activation and, as previous studies demonstrated, that hypoglycemia avoidance will lead to recovery from impaired hypoglycemia awareness [6, 7]. Therefore, an intervention which can block the propagating mechanism(s) (i.e. repeated activation of beta2-adrenergic receptors) will likely lead to improvements in hypoglycemia awareness. Previous considerations of beta-blocker use in diabetes existed; however, both retrospective and prospective studies have proven its safety [14-22]. In addition, prior insulin clamp study suggested that propranolol increased overall hypoglycemia symptom scores by increasing diaphoresis, without compromising other neurogenic and neuroglycopenic symptoms. [23] We therefore believe that propranolol is a strong testing candidate for potential impaired hypoglycemia awareness treatment.

3 DRUG INFORMATION

Propranolol (investigational drug) has been approved by FDA for indications unrelated to the current study. [24] In the current study, we will use Propranolol extended release (ER). A summary of the FDA label for propranolol has been provided in the following.

Propranolol hydrochloride is a stable, white, crystalline solid which is readily soluble in water and ethanol. Its molecular weight is 295.80. Propranolol hydrochloride extended-release capsules are formulated to provide a sustained release of propranolol hydrochloride.

Propranolol is highly lipophilic and almost completely absorbed after oral administration. However, it undergoes high first pass metabolism by the liver and on average, only about 25% of propranolol reaches the systemic circulation.

Approximately 90% of circulating propranolol is bound to plasma proteins (albumin and alpha-1-acid glycoprotein). The binding is enantiomer-selective. The S(-)-enantiomer is preferentially bound to alpha-1-glycoprotein and the R(+)-enantiomer preferentially bound to albumin. The volume of distribution of propranolol is approximately 4 liters/kg. Propranolol crosses the blood-brain barrier and the placenta, and is distributed into breast milk. Propranolol is extensively metabolized with most metabolites appearing in the urine.

Propranolol is indicated for hypertension, angina pectoris due to coronary atherosclerosis, migraine and hypertrophic subaortic stenosis.

Propranolol is contraindicated in 1) cardiogenic shock; 2) sinus bradycardia and greater than first-degree block; 3) bronchial asthma; and 4) in patients with known hypersensitivity to propranolol hydrochloride.

There have been reports of exacerbation of angina and, in some cases, myocardial infarction, following abrupt discontinuance of propranolol therapy. Therefore, when discontinuance of

propranolol is planned, the dosage should be gradually reduced over at least a few weeks, and the patient should be cautioned against interruption or cessation of therapy without the physician's advice. Since this study will be using the lowest dose of propranolol LA, and the age of the tested population imposes a lower risk of significant atherosclerotic disease, the dose will not be tapered.

Propranolol is Pregnancy Category C based on animal studies. There are no adequate and well-controlled studies in pregnant women. Intrauterine growth retardation, small placentas, and congenital abnormalities have been reported in neonates whose mothers received propranolol during pregnancy. Neonates whose mothers are receiving propranolol at parturition have exhibited bradycardia, hypoglycemia and/or respiratory depression. Adequate facilities for monitoring such infants at birth should be available. Propranolol hydrochloride extended-release capsules should be used during pregnancy only if the potential benefit justifies the potential risk to the fetus.

The following adverse events were observed and have been reported in patients using propranolol.

Cardiovascular: Bradycardia; congestive heart failure; intensification of Atrioventricular node block; hypotension; paresthesia of hands; thrombocytopenic purpura; arterial insufficiency, usually of the Raynaud type.

Central Nervous System: Light-headedness; mental depression manifested by insomnia, lassitude, weakness, fatigue; catatonia; visual disturbances; hallucinations; vivid dreams; an acute reversible syndrome characterized by disorientation for time and place, short-term memory loss, emotional lability, slightly clouded sensorium, and decreased performance on neuropsychometrics. For immediate release formulations, fatigue, lethargy, and vivid dreams appear dose related.

Gastrointestinal: Nausea, vomiting, epigastric distress, abdominal cramping, diarrhea, constipation, mesenteric arterial thrombosis, ischemic colitis.

Allergic: Hypersensitivity reactions, including anaphylactic/anaphylactoid reactions; pharyngitis and agranulocytosis; erythematous rash; fever combined with aching and sore throat; laryngospasm; respiratory distress.

Respiratory: Bronchospasm.

Hematologic: Agranulocytosis, nonthrombocytopenic purpura, and thrombocytopenic purpura.

Autoimmune: Systemic lupus erythematosus.

Skin and mucous membranes: Stevens-Johnson Syndrome, toxic epidermal necrolysis, dry eyes, exfoliative dermatitis, erythema multiforme, urticaria, alopecia, SLE-like reactions, and psoriasisiform rashes. Oculomucocutaneous syndrome involving the skin, serous membranes, and conjunctivae reported for a beta-blocker (practolol) have not been associated with propranolol.

Genitourinary: Male impotence; Peyronie's disease.

4 STUDY DESIGN

4.1 Description

The current investigation is a phase II pilot clinical trial with randomization and double-blinding design. After recruitment, the subjects will be randomized into two arms (Group 1 or Group 2), and under go a two-week assessment with Hypoglycemia Event Report and continuous glucose monitoring (CGM) with a Dexcom Professional CGM system. The subjects will then to be placed on either propranolol (Group 1) or placebo (Group 2) for a 4-week Intervention. Two weeks after the intervention is initiated, subjects will again be asked to undergo Hypoglycemic Event Report and CGM assessments for another two weeks.

4.2 Dose Limiting Toxicity

Propranolol ER will be administered at a dose of 80 mg daily during the Interventional Phase. This dose of propranolol is within the range of other indications that have been approved by FDA previously. If study subjects experience serious adverse events or intolerable toxicities determined by the PI to be related to treatment with propranolol, subjects will be discontinued from the trial, or treatment may be held for one week and resumed if adverse events resolve to a tolerable level as determined by the investigator.

4.3 Number of Subjects

Twelve patients will be enrolled and treated on this pilot study. We will use the collected information to conduct a power analysis to determine the number of subjects needed for the definitive trial.

4.4 Number of Study Centers

This study will be a single-center study conducted at the University of Utah.

4.5 Study Duration

The pilot study is expected to last for two years, and will help provide the estimated time for the final study. The duration of each patient's participation in the study will be three months.

5 ELIGIBILITY CRITERIA

This checklist is used to determine subject eligibility; it should be completed for each subject, including review and signature by the enrolling investigator and filed in the subject research chart.

Subject ID: _____

Subject Initials: _____

5.1 Inclusion Criteria

Yes/No (a response of 'No' indicates the subject is **ineligible**)

1. _____ Subjects with Type 1 diabetes for more than 5 years

2. _____ Age between 21 to 59 years old
3. _____ Hemoglobin A1C \leq 9%; most recent value within 3 months
4. _____ No beta-blocker use history in the last 6 months
5. _____ Able to provide informed consent and willing to sign an approved consent form that conforms to federal and institutional guidelines.

5.2 Exclusion Criteria

Yes/No (a response of “Yes” indicates the subject is **ineligible**)

1. _____ History of coronary, cerebral, peripheral vascular or other major cardiovascular diseases
2. _____ History of cardiac conduction abnormality or heart failure
3. _____ History of advanced kidney disease
4. _____ History of advanced liver disease
5. _____ Active malignancy
6. _____ Major Central or Peripheral Nervous System disease
7. _____ History of human immunodeficiency virus infection
8. _____ Contraindication to beta-blockers, including hypersensitivity to beta-blocker and bronchial asthma
9. _____ Female in pregnancy or not able to practice effective contraception during the study period
10. _____ Concomitant acetaminophen use
11. _____ Current use of unblinded real-time continuous glucose monitoring
12. _____ Advanced diabetic microvascular complications including retinopathy, neuropathy and nephropathy
13. _____ Inability to understand or cooperate with study procedure, including performing glucometer glucose assessment a minimum of four times a day, carrying glucose tablets and following standardized hypoglycemia treatment, completing hypoglycemia diary, wearing continuous glucose monitoring, and using a single glucometer
14. _____ Recent or current use or involvement in clinical studies of other therapies (e.g. opioid antagonist, behavioral modification, relaxation of glycemic control) that may improve hypoglycemia awareness or prevent impaired hypoglycemia awareness development

I verify that this subject meets all eligibility criteria for enrollment onto this study

Investigator Signature

Date

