9.5.2 Pregnancy Testing

Urinary pregnancy test: Qualitative Beta-human chorionic gonadotropin, urine

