9.11.5 Reporting of Pregnancy

Although pregnancy is not considered an adverse event, it is the responsibility of the PI or their designee to report any pregnancy or lactation in a subject, including the pregnancy of a male subjects' female partner as an SAE. Pregnancies or lactation that occurs during the course of the trial or within 30 days of completing the trial or starting another new therapy, whichever is earlier, must be reported to the IRB. All subjects and female partners who become pregnant must be followed to the completion/termination of the pregnancy. Pregnancy outcomes of spontaneous abortion, missed abortion, fetal death, intrauterine death, miscarriage and stillbirth must be reported as serious events.

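### The eligibility checklist is silent on breastfeeding, although the protocol says propranolol enters breast milk and makes lactation in a subject reportable

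*Combined protocol and SAP*

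**What the plan says.** Section 5 makes the checklist the instrument that decides eligibility. Its only item on reproductive status is exclusion 9 in Section 5.2: "Female in pregnancy or not able to practice effective contraception during the study period".

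Two other sections deal with lactation. Section 3 (Drug Information) states: "Propranolol crosses the blood-brain barrier and the placenta, and is distributed into breast milk". Section 9.11.5 (Reporting of Pregnancy) makes it the investigator's duty to "report any pregnancy or lactation in a subject, including the pregnancy of a male subjects' female partner as an SAE", and adds a duty to notify the IRB within a stated window.

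Treatment is one capsule daily for four weeks, blinded (Sections 6.1 and 6.3).

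**The concern.** The protocol treats lactation as a safety matter in the section on reporting but leaves it out of the rule that decides who enters. Pregnancy appears in both places. A site that follows the checklist to the letter has no written reason to turn away a woman who is breastfeeding.

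Two things are at stake. The first is possible exposure of an infant, who is not a trial participant and on whose behalf nobody is asked. The second is the safety record: with 12 subjects and an adverse-event review after every sixth completer (Section 12.2), it should be settled beforehand whether a state that a subject brought into the trial is recorded as an SAE.

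**Working it through.** There is no stated figure to reproduce. The check is a reading of the relevant sections against each other.

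1. **Is lactation in any criterion?** I read the 5 inclusion criteria, the 14 exclusion criteria and the eligibility list in the Study Summary. None mentions lactation, breastfeeding or nursing. In the whole document the subject comes up only in Section 3 and Section 9.11.5.

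2. **Does exclusion 8 reach it?** Exclusion 8 reads "Contraindication to beta-blockers, including hypersensitivity to beta-blocker and bronchial asthma". Section 3 gives the protocol's own list: "Propranolol is contraindicated in 1) cardiogenic shock; 2) sinus bradycardia and greater than first-degree block; 3) bronchial asthma", with known hypersensitivity as the fourth item. Lactation is not on it.

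3. **Would a test find it?** The only reproductive test is the one in Section 9.5.2: "Urinary pregnancy test: Qualitative Beta-human chorionic gonadotropin, urine". It is done at screening and before study drug starts (Sections 8 and 9.11.1). It detects pregnancy, not lactation.

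4. **Would a later step find it?** The withdrawal reasons in Section 6.3 and the prohibited medications and procedures in Sections 9.9.1 and 9.9.2 do not name it. Adverse-event questioning is non-directive (Section 9.11.2). No visit in the Study Calendar carries a question on breastfeeding.

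5. **A hypothetical subject.** Take a woman within the age range of 21 to 59 who is breastfeeding, uses contraception and meets the other criteria. Her answer to exclusion 9 is No, her answer to exclusion 8 is No on the protocol's own list, and her urine test is negative. She is eligible. If allocated to Group 1, she takes up to 4 × 7 = 28 daily doses, in agreement with the 28 days in Section 6.3.

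6. **Is her lactation reportable?** The text supports two readings.
   - *Reportable.* The first sentence of 9.11.5 covers any lactation in a subject, without regard to when it began.
   - *Not reportable.* The IRB sentence in 9.11.5 speaks of "Pregnancies or lactation that occurs during the course of the trial or within 30 days of completing the trial", which can mean new onset. Section 9.11.2 starts adverse-event collection after the first treatment, and counts a condition that was there before study drug only if it worsens.

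   On the first reading, the entry rule admits a state that the safety section wants reported as an SAE. On the second, lactation present at entry is neither excluded nor recorded. Both leave a gap.

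7. **Size.** The protocol gives no figure for breastfeeding among candidates. I assume 0 to 1 of 12 subjects, that is 0/12 = 0% to 1/12 = 8.3%. Exposure to propranolol also requires allocation to Group 1.

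**The case against.** The best case for leaving the text alone has four parts.

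- **A reporting duty does not imply an exclusion.** Pregnancy of a male subject's partner is reportable under 9.11.5, yet no criterion addresses it. Section 3 gives no amount or effect for milk and does not list lactation as a contraindication. This stands to a degree: the protocol's text does not compel an exclusion. It does call for an explicit decision.
- **The investigator would notice.** Charts are reviewed before selection (9.1), medical history is taken (9.4), and the enrolling investigator signs the checklist. This lowers the chance of a case, but none of these steps names lactation and no written criterion requires refusal. The consent pages are not in the copy reviewed. A warning there would not alter the checklist.
- **No SAE need arise at entry.** A reader might infer that enrolling such a woman creates an automatic SAE from the first day. The documents do not support that as a fact, because 9.11.2 and the IRB sentence of 9.11.5 allow the opposite reading. What stands is the ambiguity.
- **Harm through milk is not shown.** A reader might take Section 3's statement "Neonates whose mothers are receiving propranolol at parturition have exhibited bradycardia, hypoglycemia and/or respiratory depression" as evidence of it. That sentence concerns mothers on the drug at delivery and says nothing about exposure through milk. The point rests only on the statement that the drug reaches milk.

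**Conclusion.** The omission is real. As the checklist stands, a breastfeeding woman can be enrolled, and her infant could be exposed through milk for up to 28 days if she is allocated to propranolol. Whether her lactation would have to be reported is unsettled.

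The point is modest in frequency and rests on the assumed 0 to 1 of 12. It should be corrected because the person at risk is outside the trial. The primary outcome and its analysis (Sections 9.10.1 and 10) are not touched.

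Two further inferences should be avoided. The protocol does not treat lactation in every respect like pregnancy: 9.11.5 requires follow-up to completion and outcome reporting for pregnancy only. Nor can one case be put at one in six of an arm as an SAE rate, since the allocation ratio is not stated and the SAE itself is in doubt.

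**What to change.** Reconcile Section 5.2 with Sections 3 and 9.11.5.

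- Let the entry rule address breastfeeding alongside pregnancy, for example by adding the word to exclusion 9. Ask the question at screening and again with the Visit 2 pregnancy test.
- State in 9.11.5 that the reporting duty concerns pregnancy or lactation that arises after entry, and bring this into line with 9.11.2.
- If the sponsor means to admit breastfeeding women, say so, and say how lactation present at entry is handled and reported.

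The cost is a word in one checklist item, one question at two visits that already take place, and one clarifying sentence, submitted to the IRB as an amendment. On the assumed range, the loss of eligible subjects would be negligible.
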